Methods of monitoring clinical trials generally require knowledge of the total amount of information at trial's end. Boundaries are then constructed to guide decisions to control the probability of falsely declaring a treatment benefit at one or more interim analyses, including the final analysis. Such boundaries correspond to scenarios in which the level of evidence in support of treatment efficacy (or the lack thereof) exceeds some pre-determined threshold. Early boundaries are usually very difficult to cross, while boundaries at the end of the trial are similar to what they would be in the absence of monitoring. Our setting requires a somewhat different paradigm because although the target sample size is 100/arm, circumstances beyond our control may lead to a smaller number of patients. Moreover, we would like the flexibility of modifying the oSOC arm quite early if results show the superiority of an experimental agent plus oSOC, for example. We recommend monitoring beginning with 6 participants in an experimental arm and 6 in the best supportive care arm, and continuing after every additional patient per arm, if necessary, up to 20. After that, monitoring would be after every 20 patients per arm until the target number of 100/arm/s reached or the trial ends for other reasons. Any decision to curtail for other reasons will be made by a group blinded to trial results. The boundary we recommend is motivated from a Bayesian perspective. Bayesians formulate their prior opinion about the size of the treatment effect through a `prior' distribution, which is updated to a `posterior' distribution after observing data. We give details of the specification of the prior distribution and the construction of the boundary later. What are most important are the boundary itself and its statistical properties such as type I error rate (the probability of crossing the boundary, nappropriately, i.e., when the 2 arms are equally effective) and power (the probability of crossing the boundary appropriately, i.e., when one arm is superior to the other).

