0.1	0.5	0.82	0,09	1.00	1.00	1.00						
0.2	0.4	0.27	0.50	0.67	0.80	0.88						
0.2	0.5	0.50	0.82	0.94	0.98	1.00						
0.3	0.5	0, 2 3	0.46	0.62	0.74	0.83						

 Table 4: Probability of Crossing the Boundary for Different Mortality, Probabilities, and

 Sample Sizes in the 2 Arms

*These type I error rates refer to comparisons of two arms and do not reflect the study-wise type I error rate.

[figure not shown]
Table 5: Average Fin	al Sample Size per Arm using Stopping Criteria Defined Above
----------------------	--

	° /	1	1	8	11 8				
Mortality	Mortality	Targeted sample size (per arm)							
probability	probability	40	60	80	100				
treatment	treatment								
A (P _A)	В (Р _В)	Average	final sam	nple size (per arm)				
0.1	0.3	39	54	67	75				
0.1	0.4	35	44	48	49				
0.1	0.5	29	32	32	32				
0.2	0.4	38	56	70	82				
0.2	0.5	35	47	53	56				
0.3	0.5	38	56	71	84				

[figure not shown]
The frequency of monitoring can be altered. For example, if patient heterogeneity is large, one may not conduct the first interim analysis until more patient outcome data has accrued (e.g., 10 per arm). Regardless of the monitoring frequency, the data and safety monitoring board's recommendation to stop or continue an ongoing trial will be based on consideration of multiple factors. The Bayesian perspective allows calculation of `credibility' intervals (analogous to confidence intervals) for the difference in mortality probabilities between arms whether or not advisory boundaries are crossed.

Comparison to Other Boundaries

Even though the boundaries were motivated from a Bayesian perspective, they are actually quite similar to Haybittle-Peto boundaries using either Fisher's exact test or Barnard's test. Suppose circumstances beyond our control limit the total sample size to 20 participants per arm. A comparison of the 3 boundaries is shown, in Figures 2 and 3 for interim analyses after 10 and 15 participants, and in Figure 4 at the final analysis after 20 participants per arm. The proposed boundary is quite similar to, but slightly less conservative than, Barnard's test. Fisher's exact test is slightly more conservative.

[figure not shown]

Smaller Number

/

Figure 3: Interim Analysis after 15/Arm

Advisory Futility Boundaries

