patient per arm, if necessary, up to 20. After that, monitoring would be after every 20 patients per arm until the target number of 100/arm is reached or the trial ends for other reasons. Any decision to curtail for other reasons will be made by a group blinded to trial results. The boundary we recommend is motivated from a Bayesian perspective. Bayesians formulate their prior opinion about the size of the treatment effect through a `prior' distribution, which is updated to a `posterior' distribution after observing data. We give details of the specification of the prior distribution and the construction of the boundary later. What are most important are the boundary itself and its statistical properties such as type I error rate (the probability of crossing the boundary inappropriately, i.e., when the 2 arms are equally effective) and power (the probability of crossing the boundary appropriately, i.e., when one arm is superior to the other).

Table 10 illustrates the design's flexibility by showing the boundaries assuming that factors beyond our control result in only 20 participants per arm by trial's end instead of the planned 100 per arm (stopping boundaries for 100 subjects per arm are included in Appendix B). For example, with 6 people evaluated in each arm, we declare superiority of one arm over the other only if all 6 die in one arm and none die in the other. On the other hand, with 10 people per arm, we cross the boundary if the numbers of deaths out of 10 in the 2 arms are as follows:

- 5. 7 or more and 0,
- 6. 8 or more and 1
- 7. 9 or more and 2
- 8. 10 and 3

Notice that the boundaries at the end of the trial are more lenient than interim boundaries: interim boundaries use a probability level of 99.9%, whereas the final boundary uses a level of 97.5%. This reinforces the need for a blinded group to make stopping recommendations for reasons other than safety or efficacy; otherwise, inflation of the type I error rate could result from lowering the boundary for the final analysis. Boundaries for a sample size of 100 per group will be generated following this same procedure and will be distributed to the DSMB.

Type I Error Rate

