4.4.1.1 INTERIM MONITORING AND ANALYSES

Interim analyses will first occur after the primary outcome is available for 12 subjects. Thereafter, interim analyses will be completed every 2 subjects until outcomes are available for 40 subjects, at which points interim analyses will occur after every 40 subjects. Ideally, the treatment groups would be balanced at the interim analyses (i.e. 6/group, 7/group, etc.) but, in practice, slight imbalances are expected at any point during the trial and this will have minimal impact on the operating characteristics of the proposed interim monitoring procedure.

The following summaries will be presented at all interim analyses:

- 1. Basic summaries of 28-day survival (N and %) for each group, broken down into the following categories: dead, alive and still in follow-up period.
- 2. Point estimate and 99.8% credible interval for the absolute difference in 28-day mortality rate between the two treatment arms.
- 3. Point estimate and 99.8% credible interval for the relative risk of 28-day mortality between the two treatment arms.
- 4. The posterior probability that arm A is superior to arm B, given the observed data.
- 5. Graphical displays of the updated posterior distribution for the absolute difference and relative risk, given the observed data.

The difference in 28-day mortality will be considered statistically significant at the interim analyses if the posterior probability that the 28-day mortality rate in arm A is greater than the 28- day mortality rate in arm B is greater than 0.998 or vice versa.

Conditional power will be included in DSMB reports after outcomes are available for 40 subjects. The conditional probability will be computed as the probability of a significant result at the end of the trial, as defined in Section 4.3.1, given the current data.

A detailed description of the interim monitoring for this trial, including the rationale and operating characteristics, can be found in a separate document entitled, "Monitoring a Trial of MCMs for Ebola Virus Disease."

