On January 8, 2016, a provisional draft of the updated data analysis plan was shared with the Food and Drug Administration, Mapp Biopharmaceutical, INSERM, and other participating site investigators. The final data analysis plan detailed in the present document considers the comments that were received concerning that January 8th proposal. The document retains some of the information from the original analysis plan concerning the format and content of open and closed DSMB reports.

As of January 14, 2016, 42 days after the last case of EVD in Liberia was discharged, all three countries in West Africa had been declared Ebola-free. Accordingly, the study was planned for closure to new accrual as of that date. Subsequent to that determination there has been a potential resurgence of EVD reported in Sierra Leone; the scope and duration of that recent outbreak, as well as whether any potential new cases may be referred for enrollment, are unclear at this time. If additional enrollments do occur, this will delay the timeline for implementing the final study analysis as summarized in this document. As of the original

planned date of closure on 1-14-2016 there have been a total of 72 patients randomized on the protocol.

3 PLANNED Analyses

Unless otherwise stated, all tables, figures, and listings will show results by randomized arms. For tables with categorical variables, the number (%) will be presented. For tables with continuous variables, the mean, standard deviation, median, 25th and 75th percentiles, min and max will be presented. The number with missing values will also be shown. In calculation of percentages, subjects with missing data will not be included in the denominator. Data presented as listings or figures will be specifically noted.

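### Fifteen of the 19 planned analyses fall at 6 to 20 per arm; re-spacing the same 19 saves 3.9 to 6.4 patients per arm on average at a target of 100, with power and maximum type I error unchanged

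*Combined protocol and SAP*

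**What the plan says.** Section 7 of the protocol (Interim Monitoring), repeated in section 22 of the current version, sets the schedule. The first look is at 6 per arm: "We recommend monitoring beginning with 6 participants in an experimental arm and 6 in the best supportive care arm". Looks then go on, "continuing after every additional patient per arm, if necessary, up to 20. After that, monitoring would be after every 20 patients per arm"; section 22 carries the later part in full: "After that, monitoring would be after every 20 patients per arm until the target number of 100/arm is reached". Interim looks use a posterior probability of 99.9% and the final analysis 97.5%, in either direction, with a uniform prior in each arm.

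The Data Analysis Plan for MCM RCT (DAP), section 4.4.1.1, gives the same schedule in total subjects: first at 12, then every 2 up to 40, "at which points interim analyses will occur after every 40 subjects". Its interim level is 0.998, not 99.9%.

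The protocol gives two reasons for looking early. The trial may end well short of 100 per arm, and the team wants to be able to change the oSOC arm early. It also states that "The frequency of monitoring can be altered", with a later first look as the example. No other spacing is compared. The Final Data Analysis Plan (section 2) reports that at the planned closure date "there have been a total of 72 patients randomized on the protocol".

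**The concern.** The endpoint is death, and the protocol says the setting calls for aggressive monitoring. Yet the looks are densest where a 99.9% boundary is hardest to reach for the effects the trial is sized on, and sparsest where most crossings occur. After 20 per arm, a comparison that already meets the boundary can take in up to 20 more patients per arm before the next scheduled look. The boundary is symmetric, so the same delay applies to an agent that raises mortality. In a master protocol, any such cost recurs with each agent tested to 100 per arm.

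**Working it through.** **Inputs** (sections 7 and 22):
- Planned looks: 6, 7, ..., 20, which is 15, plus 40, 60, 80 and 100, which is 4. That makes 15 + 4 = 19 including the final analysis.
- Independent Beta(1,1) priors.
- Cross if the posterior probability that one arm has the higher mortality exceeds 0.999 at an interim look or 0.975 at the final one.
- 1:1 allocation, and no missing outcomes (assumption).

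**Method.** With x deaths in n patients, an arm's mortality has posterior Beta(1+x, 1+n−x). The joint distribution of the two death counts is carried exactly from look to look, removing the outcomes that cross. Power, or type I error when the arms are equal, is Σ P(first cross at look k). Average n per arm is Σ n_k · P(stop at look k), with trials that never cross counted at the maximum.

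**The plan's own figures reproduce.** Power at 100 per arm is 0.879 (0.2 v 0.4) and 0.834 (0.3 v 0.5), against 0.88 and 0.83 stated. Type I error runs from 0.0475 to 0.0637, against simulated values of 0.048 to 0.063. Average n matches Table 5/12 in all six scenarios. The sentence under Power and Sample Size giving 76 per arm for 0.3 v 0.5 does not reproduce; the table's 84 does.

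**Re-spaced looks:** 6, 8, 10, 12, 15, 20 (6 looks); 25, 30, ..., 70 (10 looks); 80, 90, 100 (3 looks). 6 + 10 + 3 = 19. Thresholds are unchanged.

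| Mortality | Table 5/12 | Planned, exact | Re-spaced | Saving per arm | Crossed by 20 per arm (planned) |
|---|---|---|---|---|---|
| 0.1 v 0.3 | 75 | 75.0 | 68.8 | 6.2 | 5.6% |
| 0.1 v 0.4 | 49 | 48.8 | 42.5 | 6.3 | 19.9% |
| 0.1 v 0.5 | 32 | 32.2 | 27.9 | 4.3 | 43.3% |
| 0.2 v 0.4 | 82 | 81.6 | 77.0 | 4.6 | 5.9% |
| 0.2 v 0.5 | 56 | 56.1 | 49.7 | 6.4 | 17.6% |
| 0.3 v 0.5 | 84 | 83.9 | 80.0 | 3.9 | 6.0% |

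Savings are differences of the rounded entries. Over both arms they come to 2 × 3.9 = 7.8 up to 2 × 6.4 = 12.8 patients per comparison.

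**Error rates at 100 per arm.** Power goes from 0.8789 to 0.8793 (0.2 v 0.4) and from 0.8342 to 0.8348 (0.3 v 0.5). Maximum type I error goes from 0.0637 to 0.0636. At mortality 0.1 to 0.2 type I error rises by about 0.1 point; the largest rise is at 0.2, from 0.0512 to 0.0523.

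**Dependence on final size** (six scenarios, saving per arm):

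| Final n per arm | Saving |
|---|---|
| 100 | 3.9 to 6.4 |
| 60 | 1.5 to 4.7 |
| 40 | 0.3 to 2.6 |
| 36 (72/2, assuming an even split) | 0.1 to 1.2 |
| 20 | negative: up to 0.8 more per arm |

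If the trial is cut off at 36 to 40 per arm, power falls by at most 0.2 points. Under the null there is no saving, and for 10-point differences (0.3 v 0.4, 0.4 v 0.5) it is under 1 per arm even at 100.

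**Patients still inside the 28-day window.** The averages count patients with known outcome. If 10 or 20 per arm are in the window when the trial stops (assumptions), the enrolment saving at 0.3 v 0.5 is 3.1 or 2.8, and at 0.2 v 0.4 it is 3.6 or 3.3. The trial's own pace was slower: 72 patients from 13 March to 21 November 2015 (253 days) gives 72 × 28/253 ≈ 8, or about 4 per arm per 28 days.

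**Sensitivity to the choice of schedule.** A 19-look schedule at 10, 15, ..., 100 saves 3.8 to 6.8, or 3.0 to 6.9 with the DAP's 0.998. Four other 19-look schedules save 2.8 to 7.2. The result does not hinge on one particular set of looks.

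**The case against.** **The early looks are a stated choice.** The protocol wants them in case numbers fall short and so that oSOC can change early. That stands as a priority, and re-spacing gives up a little of it. Crossing by 20 per arm falls from 0.433 to 0.396 at 0.1 v 0.5 and from 0.059 to 0.046 at 0.2 v 0.4. Because looks at 6, 8, 10 and 12 remain, crossing by 12 per arm barely moves: 16.4% to 15.7%, and 2.1% to 1.9%. At 0.1 v 0.8 the trial stops about 0.75 per arm later. If the trial is curtailed at 20 per arm, average size rises by 1.03 (0.1 v 0.8) and 1.15 (0.2 v 0.8).

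**Early crossing is not rare in general.** A reader might infer that the 15 early looks are idle. The figures do not support that: 18 to 20% cross by 20 per arm for 30-point effects, 43% for 0.1 v 0.5 and 87% for 0.2 v 0.8. The 6% figure belongs to 20-point effects.

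**The trial never came near 100 per arm.** A reader might infer that it enrolled 4 to 6 patients per arm too many. At 36 per arm the expected saving is 0.1 to 1.2, so that inference fails. The larger figure applies only to a comparison that aims for 100.

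**Flexibility already exists.** The frequency may be altered, the boundaries are advisory, and the DSMB may convene extra reviews and pause enrolment for safety (section 26.9.3); it reviewed interim data seven times. So a reader would be wrong to infer that nobody could look for harm between 20 and 40 per arm. Only the formal boundary schedule has that gap. Discretionary reviews, however, come with no specified look times or calculated error rates.

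**Conclusion.** The point holds as an efficiency improvement. It rests on a target of 100 per arm, the protocol's 99.9% and 97.5% levels, uniform priors, looks with equal numbers per arm, and outcomes known at each look. Under those conditions the same number of analyses, spaced differently, gives a smaller average trial in all six protocol scenarios at no cost in power or maximum type I error. The price is slightly later stopping for extreme effects and a slightly larger trial if it ends at about 20 per arm. A reader might take the schedule for a mistake. It is not: it is internally consistent, its stated operating characteristics reproduce in Tables 4/11 and 5/12, and its early emphasis is explained. What is missing is a comparison with any other spacing.

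**What to change.** In section 22 (Interim Monitoring) and DAP 4.4.1.1:
- Set the formal boundary looks at 6, 8, 10, 12, 15 and 20 per arm, then every 5 per arm to 70, then 80, 90 and 100.
- Keep the protocol's 99.9% interim and 97.5% final levels, and reconcile the DAP's 0.998 with the protocol. With the planned looks, 0.998 gives an exact maximum type I error of 7.1%.
- Leave conditional-power reporting as the DAP has it, once outcomes are available for 40 subjects.
- Regenerate Tables 11 and 12 and Appendix B, and bring the 76-per-arm sentence into line with Table 12.

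The cost is wording and recomputation, with no additional analyses if the trial runs to 100 per arm. The change matters mainly for a later comparison that expects to go well beyond 40 per arm.

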8 RISKS AND BENEFITS

Potential Risks

8.1.1 Unknown Risks

The primary risks to participants are due to study interventions whose human safety profile is either absent or, in most cases, early and accumulating, due to ongoing animal and/or early/first in human trials. Generally these are either still in early phase 1 testing, have not yet entered phase 1 testing, or, for those interventions in more advanced development, have not yet been tested in a human population infected with Ebola virus. Thus, unlike conventional phase 2 trials in which a safety database has already been generated to guide the dosing and schedule of study drug administration, it is presently unknown what toxicities these agents could cause when used in this critically ill patient population or, for that matter, in any humans at all.

It is anticipated that additional animal safety and toxicity studies will be in-progress at the time of trial initiation for some agents. Results will be made available to the study investigation team and pertinent regulatory bodies for review promptly, as they are available. In addition, in some cases phase 1 testing of lead candidates in normal human volunteers may commence during the same interval of time that this trial is conducted. Should it be concluded from any of these studies that there are additional significant risks to study subjects, participants will be informed and additional administration of study product may be suspended until review by the FDA as well as by each institution's IRB.

8.1.2 Risks of Phlebotomy

The primary risks of phlebotomy include local discomfort, occasional bleeding or bruising of the skin at the site of needle puncture, hematoma and, rarely, infection or fainting. Because ongoing clinical care of participants may require frequent blood draws independent of actual study-related assessments, it will be important that study teams ensure that research blood draws do not exceed the guidelines set forth by each institution's safety regulations.

8.1.3 Risks to the Study Personnel and the Environment

The principal risk for study personnel is exposure in the clinical setting to infectious pathogens from study subjects through various contact mechanisms (e.g., needlestick or mucous membrane exposure to blood borne pathogens or infected bodily fluids). Adherence to mandatory hygiene practices and infection control practices, including consistent and appropriate use of PPE, for working with patients infected with Ebola is of absolutely paramount importance throughout the conduct of this trial. Any perceived break in those practices must be reported immediately to the appropriate supervisory authorities in each institution per established algorithms.

Potential Benefits

There is no definite expectation of benefit to participants or to society at large. However, the agents likely to be investigated in this study are all thought to have some potential to offer benefits to individual subjects, based upon previous pre-clinical and in some cases clinical investigation. Hence, while the potential benefits, if any, of a given medical intervention are presently unknown, it is conceivable that one or more interventions may subsequently be shown to offer evidence of a greater reduction in morbidity and mortality than that provided by oSOC alone. This may be manifested by a reduction in the length or the severity of disease, which may be life-saving in some cases given the nature of Ebola infection. If this is so, it is quite possible that this evidence will be suggestive, but not definitive, at this very early stage of testing. However, even if no experimental treatment intervention is shown to provide this benefit, the knowledge gained from their study will provide important information that should help better inform what role such interventions should or should not play as adjunctive treatments in managing this disease. Thus, it is possible that both positive and negative results will help inform rapidly evolving treatment paradigms, and thus may offer a societal benefit.

Alternatives

The alternative to participating in this protocol is not to participate and to receive access either to supportive care measures or to experimental therapies through other approved regulatory means.

9 RESEARCH USE OF STORED HUMAN SAMPLES, SPECIMENS, AND DATA

Intended Use of the Samples/Specimens/Data

Samples and data collected under this protocol will be used to determine the safety, immunogenicity, and antiviral effects of the treatment interventions.

Storage of Samples/Specimens/Data

Samples obtained in this study must adhere to CDC regulations governing the storage of blood obtained from patients infected with Select Agents in other than BSL-4 containment facilities, which specifically require documentation of destruction of potentially infectious samples after more than 7 days time according to established CDC guidelines. Whenever possible, sites which have access to a secure BSL-4 laboratory repository should attempt to transfer samples to that repository for longer-term storage according to approved shipping regulations applicable to select agents.

In the future, other investigators (both at NIH and outside) may wish to study these samples and/or data. In that case, IRB approval must be sought prior to any sharing of samples. Any clinical information shared about the sample with or without patient identifiers would similarly require prior IRB approval.

The research use of stored, unlinked or unidentified samples may be exempt from the need for prospective IRB review and approval. Exemption requests will be submitted in writing to the NIH Office of Human Subjects Research, which is authorized to determine whether a research activity is exempt.

Storage of Genetic Samples

No samples are being stored for genetic testing on the subjects.

Reporting Loss or Destruction of Samples/Specimens/Data

Any loss or unanticipated destruction of locally maintained samples (for example, due to freezer malfunction) or data (for example, misplacing a printout of data with identifiers) will be reported to the institution's IRB and to the protocol team.

